4.3 Follow-up procedures (by visits)

*N.B.: virtual after 3/20.

- 3-Month Follow-Up
 - Vitals (Patient, Partner)

- Height, weight, BMI, blood pressure, heart rate
- Questionnaire (Patient, Partner)
 - EDE-Q, BES, BE frequency, BDI-II, BAI, DERS, DERS-Partner, DAS, CPQ-SF, R-BISF, MSI-R, EDQOL
- \$50 visa card upon completion
- 6-Month Follow-Up
 - Vitals (Patient, Partner)
 - Self-reported height, weight, BM
 - Questionnaire (Patient, Partner)
 - EDE-Q, BES, BE frequency, BDI-II, BAI, DERS, DERS-Partner, DAS, CPQ-SF, R-BISF, MSI-R, EDQOL
 - YBOCS-BE Interview (Patient)
 - \$50 visa card upon completion

4.4 Subject Withdrawal procedures

Decisions regarding study withdrawal will be made by the investigators. Factors to consider include:

- (a) physical deterioration or escalation of symptoms requiring prolonged hospitalization
- (b) couple separates and is no longer in a committed relationship.
- (c) significant risk of suicide in the judgment of the treatment provider
- (d) development or exacerbation of a severe comorbid psychiatric disorder, such as a psychotic disorder or severe major depressive disorder, making it unlikely that they would benefit from outpatient treatment.

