---------------------------	---

Outcomes	
Primary outcome: Eating Disorder Examination-Questionnaire (EDE-Q) abstinence from binge eating (Fairburn & Beglin, 1994).
 
Secondary outcomes will include ED symptoms, depression and anxiety, couple-based measures, treatment satisfaction, and quality of life. ED symptoms will be measured with the Eating Disorder Examination-Questionnaire (EDE-Q; 28 items) binge frequency and global score (Fairburn & Beglin, 1994), the Binge Eating Scale (BES; 16 items) which measures binge eating severity (Gormally et al., 1982), and the Yale-Brown Obsessive Compulsive Scale Modified for Binge Eating (Y-BOCS-BE; 10 items) which measures the obsessiveness of binge-eating thoughts and compulsiveness of binge-eating behaviors (Deal et al., 2015). Beck Depression Inventory-II (BDI-II; 21 items) and Beck Anxiety Inventory (BAI; 21 items) will measure severity of current depressive and anxiety symptoms, respectively (Beck et al., 1988; Beck et al., 1996). Difficulties in Emotion Regulation Scale (DERS; 36-item) and the partner version (DERS-Partner; 8 items) will measure emotion regulation in oneself and one's partner, respectively (Gratz & Roemer, 2004). Dyadic Adjustment Scale (DAS; 32 items) and DAS-4 (4 items) will measure relationship satisfaction. Communication Patterns Questionnaire-Short Form (CPQ-SF; 12 items (Christensen & Heavey, 1990) modified for BED has two scores that will be calculated to assess how the couple communicates about the ED. These are a total score made up of the Self Demand/Partner Withdraw and Partner Demand/Self Withdraw subscales (6 items) and the Constructive Communication subscale (3 items). Marital Satisfaction Inventory (MSI-R; 32 items) affective communication (AFC) and problem-solving/communication (PSC) subscales will be used (Snyder, 1997). Treatment satisfaction will be measured with the Client Satisfaction Questionnaire (CSQ; 18 items). (Nguyen et al., 1983). Eating

-----------------	---

Disorders Quality of Life (EDQOL; 26 items) will measure the extent to which the ED affects quality of life (Engel, 2003). ED-related measures will be given to patients only and all other measures will be given to patients and partners.	

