3.2 Study Duration, Enrollment and Number of Subjects

38 couples will be enrolled over 18 months (to aim for 34 couples who complete the intervention). Each couple will be randomized to either UNITE or CBT-E and will undergo 16 weeks of treatment, followed by follow-up assessments at the end of treatment and 3- and 6-months after the end of treatment.

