4.2 Intervention/Treatment procedures (by visits)

Both UNITE and CBT-E have 16 treatment sessions

Weekly questionnaires to be completed by the participants in treatment

Weekly Questionnaires consist of binge eating frequency assessment, DAS-4

For UNITE, Patient and Partner fill out questionnaires. For CBT-E, only Patient.

Mid-treatment assessment after session 8 is completed

End-treatment assessment after session 16 is completed

Mid-Treatment (after Session 8)

- Vitals (Patient, Partner)
 - Self-reported height, weight, BMI
- Questionnaire (Patient, Partner)
 - EDE-Q, BES, BE frequency, BDI-II, BAI, DERS, DERS-Partner, DAS, CPQ-SF, R-BISF, MSI-R, EDQOL
- Check BDI for suicidality
- YBOCS-BE Interview (Patient)

Post-Treatment (after Session 16)

- **Couple Interaction**
- Vitals (Patient, Partner)
 - Self-reported height, weight, BMI
- Questionnaire (Patient, Partner)
 - CSQ, EDE-Q, BES, BE frequency, BDI-II, BAI, DERS, DERS-Partner, DAS, CPQ-SF, R-BISF, MSI-R, EDQOL
- YBOCS-BE Interview (Patient)
- Therapist Feedback (Therapist)

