5.3 Statistical Methods

- **Baseline Data.** Sociodemographics and baseline clinical characteristics will be summarized with descriptive statistics.
- **Efficacy Analysis.** Study hypotheses will be tested using intent-to-treat or modified intent-to-treat methods, as appropriate. For patient-only outcomes, differential treatment effects will be tested with multilevel mixed-effects models with fixed effects and two-way interactions for Time and Treatment and a random effect for Patient. For outcomes assessed in both patients and partners, differential treatment effects will be tested with multilevel mixed-effects models with fixed effects and two- and

three-way interactions for Time, Treatment, and Participant Status (i.e., Patient or Partners) and random effects for Participant and Couple. Linear, logistic, and Poisson distribution functions will be used to model outcome variables. Treatment satisfaction, assessed at post-treatment only, will be compared between patients in UNITE and CBT-E with linear regression.

- **Safety Analysis.** Adverse events will be summarized as a numerator (total affected) and denominator (number at risk) for patients and partners in each treatment arm using the ClinicalTrials.gov categories of all-cause mortality, serious adverse events, and other (not including serious) adverse events.

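### Nothing in the plan keeps patients who stop treatment or are withdrawn in EDE-Q assessment, so the abstinence comparison can lose primary-outcome data for outcome-related reasons, with no sensitivity analysis planned

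*Combined protocol and SAP*

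**What the plan says.** - **Withdrawal (section 4.4).** "Decisions regarding study withdrawal will be made by the investigators". The factors to weigh are deterioration or symptom escalation leading to prolonged hospitalisation, suicide risk, severe psychiatric comorbidity, and that the "couple separates and is no longer in a committed relationship". The section does not distinguish stopping treatment from leaving the study, and it is silent on outcome collection afterwards.
- **Assessment timing.** Section 4.2: "End-treatment assessment after session 16 is completed". Section 3.2 says that couples "will undergo 16 weeks of treatment, followed by follow-up assessments at the end of treatment", which suggests a nominal week 16. Neither gives a time for a patient who stops early.
- **Weekly form (section 4.2).** "Weekly questionnaires to be completed by the participants in treatment". It stops with treatment, so it does not replace the EDE-Q.
- **Who completes the EDE-Q.** Synopsis, Outcomes: "ED-related measures will be given to patients only and all other measures will be given to patients and partners". Table 3 also codes the EDE-Q for the patient alone at every visit. The visit lists in sections 4.1 to 4.3 put it under a joint patient-and-partner line, but nothing makes the patient's form depend on the partner.
- **Analysis (section 5.3).** For patient-only outcomes, a mixed model with "fixed effects and two-way interactions for Time and Treatment and a random effect for Patient". The analysis set is intent-to-treat or a modified version that is not defined. No missing-data assumption or sensitivity analysis is stated. Section 5.5 accepts that dropout and missing data could limit the analysis, and offers no remedy.

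**The concern.** The primary outcome is 28-day abstinence on the EDE-Q. Several section 4.4 factors are plausibly related to it: a patient withdrawn for worsening symptoms or severe comorbidity is unlikely to have the same chance of abstinence as one who stays. The mixed model uses whatever visits are available, which is valid only if the missingness is explained by the data in the model. A withdrawal made on these grounds may carry information that earlier EDE-Q values do not.

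Separation is the clearest case. It may end the couple measures, but it is no reason to stop asking the patient about binge eating. It is also a factor that could differ by arm, since only UNITE works on the relationship.

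At stake is the estimated difference between arms, which is the main product of a trial looking for preliminary evidence of superiority.

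**Working it through.** **The plan's own figure.** Section 3.2: "38 couples will be enrolled over 18 months (to aim for 34 couples who complete the intervention". The implied loss is 4/38 = 10.5%, and 34/(1 - 0.105) = 38. No dropout rate is stated, so this shows consistency only. The allowance concerns completing the intervention. It is not a count of section 4.4 withdrawals or of missing EDE-Qs.

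**Inputs.** From the documents: 38 couples randomised 1:1 (section 7), so 19 patients per arm. Assumed, because the documents give none: true abstinence p of 30-60%, equal in both arms; four patients without a post-treatment EDE-Q; analysis of observed proportions only.

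**1. Equal true abstinence, all four losses non-abstinent.** With w1 and w2 losses, the false difference is 19p/(19 - w1) - 19p/(19 - w2).

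| Split | p = 0.30 | p = 0.60 |
|---|---|---|
| 2:2 | 0 | 0 |
| 3:1 | 5.7/16 - 5.7/18 = 4.0 points | 11.4/16 - 11.4/18 = 7.9 points |
| 4:0 | 5.7/15 - 5.7/19 = 8.0 points | 11.4/15 - 11.4/19 = 16.0 points |

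The arm with more losses looks better.

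**2. Milder case: 75% of losses non-abstinent.** The observed rate is (19p - 0.25w)/(19 - w). The false difference is 0.7-4.6 points for 3:1 and 1.3-9.3 points for 4:0.

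**3. Equal losses, unequal true abstinence.** Assume 60% v 40% and two non-abstinent losses in each arm. Observed rates are 11.4/17 = 67.1% and 7.6/17 = 44.7%. The difference is 22.4 points instead of 20, and the odds ratio is 2.52 instead of 2.25. The zero in the 2:2 row therefore depends on equal true rates.

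**4. Scale.** SE of the difference = sqrt(2p(1 - p)/19) = 14.9 points at p = 0.30, 16.2 at 0.50 and 15.9 at 0.60; the 95% half-width is 29.1-31.8. A 3:1 split gives 4.0/14.9 = 0.27 to 7.9/15.9 = 0.50 SE. A 4:0 split gives 8.0/14.9 = 0.54 to 16.0/15.9 = 1.0 SE.

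**5. What missing outcomes leave open.** Each unobserved patient leaves 1/19 = 5.3 points of the difference undetermined. Four leave 4/19 = 21.1 points between best and worst case, however they split.

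**6. Counting missing as non-abstinent.** If a 4:0 loss is unrelated to outcome, this rule itself shifts the difference by -4p/19, that is 6.3 to 12.6 points against the arm with the losses.

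**The case against.** The strongest reply is that this argues from silence. Section 4.4 lists matters to consider in a discretionary decision and does not say that assessment ends. Follow-up is scheduled for participants generally, not for completers only. Intent-to-treat is named first, and the mixed model can draw on a mid-treatment EDE-Q. Eligibility already excludes active suicidal intent, severe depression and unstable psychosis, so some factors should seldom arise. No document shows that losses will differ by arm. The largest figure needs a 4:0 split, four non-abstinent losses and 60% abstinence together; if four losses fell at random, a 4:0 split in either direction has probability 2 × C(19,4)/C(38,4) = 10.5%. The trial is preliminary, and most of the illustrated bias is below one SE.

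Much of this stands. A reader might infer that the plan discards withdrawn patients, or that UNITE and CBT-E will lose different numbers. The documents support neither: continued collection is not stated, and differential loss is plausible but not shown.

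The rest does not answer the point. Intent-to-treat protects the comparison only if outcomes are obtained or their absence is handled, and the undefined modified set could leave these patients out. The model's protection may be thin for early losses. Everyone enters with current BED, so baseline abstinence should barely vary (an inference), and a patient lost before session 8 adds almost nothing specific about abstinence. A systematic shift smaller than one SE is still a shift in the estimate.

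**Conclusion.** The gap is real and worth closing. Followed as written, the plan can lose the primary outcome for outcome-related reasons, including separation, when the measure needs only the patient.

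Bias in the UNITE versus CBT-E difference can arise if such losses differ by arm, or with equal losses when true abstinence differs. A reader might infer that balanced losses are harmless. That holds in this illustration only when the arms have equal true abstinence, and the trial hypothesises that they do not.

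The size is unknown because no withdrawal rates are given. The 0, 4-8 and 8-16 point figures are crude proportions under assumed abstinence and a borrowed count of four losses. They are not estimates from the planned mixed model, which may remove part of the effect. True missingness could be lower or higher.

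**What to change.** Leave the section 4.4 factors and all treatment decisions as they are.

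1. **Section 4.4.** State that stopping treatment or a withdrawal decision does not end EDE-Q collection unless consent is withdrawn. Ask patients who stop early for the EDE-Q remotely at nominal week 16 and 3 and 6 months later. Keep completers on the session-16-based schedule: a calendar rule for everyone would assess some completers before treatment ended if their sessions ran late. Couple measures may lapse on separation.
2. **Section 5.3, analysis set.** Make all randomised patients the primary set. Define any modified set in advance, as secondary.
3. **Section 5.3, sensitivity.** Count missing abstinence as non-abstinent, and show it beside best-case and worst-case bounds because that rule can itself mislead (step 6 of the working). These analyses show how far missing data could move the result; they do not detect bias.
4. **Reporting.** Give withdrawals by arm and reason.

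The cost is a short amendment and a few extra questionnaires, which are easy to send because follow-up is virtual after 3/20 (section 4.3). Some withdrawn patients will refuse. Section 6 describes part of the conduct in the past tense. If follow-up has ended, lost data cannot be recovered and only items 2 to 4 remain. Analysis changes made after data by arm were seen must then be labelled post hoc.

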4.5 Screen Failure procedures

Participants who are ineligible for this study will be provided with treatment referral information.

5 STUDY EVALUATIONS AND MEASUREMENTS

5.1 Efficacy Evaluation

Preliminary efficacy (e.g. changes in binge-eating frequency, depression, anxiety, and relationship functioning) of UNITE will be assessed in comparison to the control group (CBT-E). Treatment gains will be assessed including observational and self-report measures. The primary outcome is abstinence from binge eating over the past 28 days measured with the EDE-Q. Secondary outcomes include EDE-Q binge frequency and global psychopathology, BES, Y-BOCS-BE, BDI-II, BAI, DERS, DERS-Partner, DAS, DAS-4, CPQ-SF, MSI-R (AFC and PSC), CSQ, and EDQOL.

5.2 Safety Evaluations

Weekly reports from therapists to supervisors on therapy progress and from staff on assessments and follow-up visits. Discussed by investigators at weekly team meetings.

STATISTICAL CONSIDERATIONS

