1 BACKGROUND AND RATIONALE

1.1 Introduction

Clinicians' options for EDs (ED) treatment are inadequate. EDs challenge caregivers and strain relationships (Van den Broucke & Vandereycken, 1988; Van den Broucke et al., 1994, 1995, 1995; Whisman et al., 2012). Partners are typically excluded from treatment. Family involvement improves outcomes in youth (Ie Grange et al., 2010) and in adults with anorexia nervosa (AN) (Baucom et al., 2017). Engaging partners improves weight gain in AN, reduces high drop out in AN (Baucom et al., 2017) and binge-eating disorder (BED) (Runfola et al., 2018), and may lead to greater binge-eating abstinence (Runfola et al., 2018). As BED awareness and treatment demand increases post DSM-5, the field will benefit from scalable interventions.

- Name and Description of Intervention: The experimental treatment, UNITE, is a manualized cognitive-behavioral couple therapy (CBCT) intervention that engages the couple to address the core psychopathology of BED. It includes three stages: early treatment (psychoeducation and understanding the couple's experience of BED within the relationship); mid-treatment (effective communication, interpersonal problem-solving, and emotion regulation skills), and late treatment (relapse prevention). Additional relevant topics may be covered including body image, weight stigma, weight and health concerns, and intimacy and sexuality issues.

The active comparator, CBT-E, is a trans-diagnostic cognitive behavioral individual therapy treatment for eating disorders. It has been shown to be effective in numerous controlled and open trials. It includes four stages: an introductory stage (psychoeducation, normalization of eating patterns, and symptom self-monitoring); a second, brief stage (review progress and formulate plans for the subsequent treatment phase); a third stage (elimination of dieting, reducing shape checking and avoidance behaviors, educating about mood tolerance, and targeting over-evaluation of shape and weight); and the fourth stage (maintaining progress and minimizing relapse risk).

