Van den Broucke, S., Vandereycken, W., & Vertommen, H. (1994). Psychological distress in husbands of eating disorder patients. *Am J Orthopsychiatry*, 64(2), 270-279.
http://www.ncbi.nlm.nih.gov/entrez/query.fcgi?cmd=Retrieve&db=PubMed&dopt=Citation&list_uids=8037235

Van den Broucke, S., Vandereycken, W., & Vertommen, H. (1995). Marital communication in eating disorder patients: a controlled observational study. *Int J Eat Disord*, 17(1), 1-21.
http://www.ncbi.nlm.nih.gov/entrez/query.fcgi?cmd=Retrieve&db=PubMed&dopt=Citation&list_uids=7894447

Van den Broucke, S., Vandereycken, W., & Vertommen, H. (1995). Marital intimacy in patients with an eating disorder: a controlled self-report study. *Br J Clin Psychol*, 34 (Pt 1), 67-78.
http://www.ncbi.nlm.nih.gov/entrez/query.fcgi?cmd=Retrieve&db=PubMed&dopt=Citation&list_uids=7757040

Whisman, M. A., Dementyeva, A., Baucom, D. H., & Bulik, C. M. (2012). Marital functioning and binge eating disorder in married women. *The International journal of eating disorders*, 45(3), 385-389. <https://doi.org/10.1002/eat.20935>

Table 1.**Comparison of Intervention Arms**

Table 1: Comparison of Intervention Arms		
Discipline	UNITE (16 sessions)	Individual CBT-E (16 sessions)
Medical	Psychiatrist (1)	Psychiatrist (1)
	Medical consults (as needed)	Medical consults (as needed)
Psycho-therapy	UNITE Couple Sessions (one 120-minute intro session, one 90-minute second session and fourteen 60 minute sessions) 1050 minutes	Individual CBT-E (one 120-minute intro session, one 90-minute second session and fourteen 60 minute sessions) 1050 minutes

Table 2.**UNITE Manual Components**

Table 2. UNITE Manual Components	
Session	Topic
Early Treatment	
1	Introduction to UNITE and Relationship Assessment
2	Understanding BED in a Couples Context: Symptoms and Course of Illness
3	BED Etiology, Treatment Goals, and Recovery
Mid-Treatment	

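### The by-arm summary of partner adverse events is open to ascertainment bias, because therapists meet partners only in UNITE and no common adverse-event question is scheduled.

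*Combined protocol and SAP*

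**What the plan says.** - **Reporting.** Section 5.3 (Safety Analysis): "Adverse events will be summarized as a numerator (total affected) and denominator (number at risk) for patients and partners in each treatment arm". The categories are deaths, serious events and other, non-serious events. No test or between-arm contrast is named.
- **Sources.** Section 5.2 gives two: "Weekly reports from therapists to supervisors on therapy progress and from staff on assessments and follow-up visits". The investigators discuss these at weekly meetings.
- **Sessions.** Section 4.2: "Both UNITE and CBT-E have 16 treatment sessions". Table 1 describes one arm as "UNITE Couple Sessions (one 120-minute intro session, one 90-minute second session and fourteen 60 minute sessions) 1050 minutes" and the other as "Individual CBT-E (one 120-minute intro session, one 90-minute second session and fourteen 60 minute sessions) 1050 minutes". Section 1.1 states that "CBT-E, is a trans-diagnostic cognitive behavioral individual therapy treatment for eating disorders".
- **Weekly questionnaires.** Section 4.2: "For UNITE, Patient and Partner fill out questionnaires. For CBT-E, only Patient". Their content is binge frequency and the DAS-4.
- **Shared assessments.** Sections 4.2 and 4.3 and Table 3 schedule partners in both arms at mid-treatment, post-treatment, 3 months and 6 months, with BDI-II, BAI, DERS and DAS among the measures.
- **Eliciting events.** No adverse-event question or form appears in the visit lists of Sections 4.1 to 4.3 or in Table 3. Section 8 covers the reporting of events once known, not how they are to be found.

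**The concern.** The denominators treat partners in the two arms as equally observed. By design they are not. A UNITE partner sits with a therapist about once a week for 16 weeks. A CBT-E partner attends no sessions, so the CBT-E therapist can learn of a partner event only second-hand, through the patient. With no standard question, a non-serious event enters the record when it happens to come up in contact, and UNITE partners have more occasions for that.

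Bringing the partner into treatment is what UNITE adds, and Section 1.2 accepts that the couple format may be uncomfortable for some. A reader will look at the partner columns for signs of harm. An excess in UNITE could be a real effect, closer observation or both, and the table as planned gives no means of separating them. The likely direction is against UNITE. The problem lies mostly in the non-serious category, because deaths and serious events are more likely to become known without weekly contact.

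**Working it through.** **1. Therapy time (Table 1).** 120 + 90 + 14 × 60 = 1050 minutes, which reproduces the stated figure in both arms. Therapist time with the partner present is therefore 1050 minutes in UNITE and 0 in CBT-E.

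**2. Planned partner contacts after baseline** (sessions from Section 4.2 and Table 1; assessments from Sections 4.2 and 4.3 and Table 3):

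| | UNITE | CBT-E |
|---|---|---|
| Therapy sessions | 16 | 0 |
| Mid and Post | 2 | 2 |
| Subtotal in treatment | 18 | 2 |
| 3 and 6 months | 2 | 2 |
| Total | 20 | 4 |

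This assumes full attendance by UNITE partners and no partner attendance at CBT-E sessions. Weekly questionnaires are left out because their content is not an adverse-event screen. Restricted to the assessments that both arms share, the count is 4 against 4.

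**3. From contacts to recorded events.** The documents give no event rate and no detection rate, so both are assumed here. Suppose true rates are equal, and each of k contacts reveals an event independently with probability q. Detection is then 1 − (1 − q)^k, with k = 20 in UNITE and k = 4 in CBT-E. This treats an event as discoverable at every contact.

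| q | UNITE | CBT-E | Apparent ratio |
|---|---|---|---|
| 0.05 | 0.642 | 0.185 | 3.5 |
| 0.10 | 0.878 | 0.344 | 2.6 |
| 0.20 | 0.988 | 0.590 | 1.7 |
| 0.50 | 1.000 | 0.938 | 1.07 |

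The distortion is large if contacts reveal little and almost disappears if each assessment elicits events well.

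**4. In counts.** With 38 couples allocated 1:1, take 19 partners per arm. Assume a true risk of 20% in both arms.
- Detection 90% v 50%: 19 × 0.20 × 0.90 = 3.4 affected in UNITE and 19 × 0.20 × 0.50 = 1.9 in CBT-E, a ratio of 1.8 and a difference of 8 percentage points.
- Detection 100% v 80%: 3.8 v 3.0, a ratio of 1.25.
- For true risks from 10% to 40% at 90% v 50%, the difference is 0.10 × 0.40 = 4 points up to 0.40 × 0.40 = 16 points.

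At 19 per arm, a two-sided 5% test would call the 90% v 50% difference significant only about 7% to 19% of the time over these risks. The threat is to how the raw counts are read, not mainly a false significant result.

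**The case against.** The strongest reply is that no comparison is planned. Section 5.3 tests efficacy hypotheses and compares satisfaction between arms, but adverse events are only summarised. That stands: a reader might infer that partner events are compared formally, or that this table is the direct test of whether UNITE harms partners, and the documents support neither. Counts with denominators set out by arm still invite a comparison.

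Second, partners are followed symmetrically elsewhere. BDI-II, BAI, DERS and DAS are scheduled for partners at the same assessments in both arms, and Section 5.3 models such outcomes by Time, Treatment and Participant Status. This also stands. It gives balanced evidence on worsening mood or relationship satisfaction, but not on other kinds of event.

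Third, CBT-E partners are not unobserved. Staff reports on assessments are the other source in Section 5.2, the Synopsis (Safety Evaluations) commits to monitoring all participants, and the mid-treatment suicidality check carries no arm restriction. It would therefore be wrong to say that a low CBT-E count means nothing; it would be less sensitive. For the same reason the documents do not support the reading that the table shows observation rather than how partners fare.

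Fourth, unequal contact is inherent in couple against individual therapy, and the contact count weights a session and an assessment alike. Both points are true. They limit what can be said about size, but do not explain why no common question is asked at the assessments that the arms share.

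**Conclusion.** The concern holds as a weakness in ascertainment and reporting. One of the two stated safety sources has direct contact with partners only in UNITE, planned partner contacts after baseline are about 20 against 4, and no uniform elicitation is scheduled in either arm. The partner counts will mix true events with the chance of hearing about them, chiefly in the non-serious category.

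The split between the two cannot be calculated from the documents. Under the assumed per-contact model, the apparent ratio with equal true rates runs from 3.5 to 1.07, so the distortion may be large or almost nil. The contact counts rest on the planned schedule with full attendance, and the direction rests on detection rising with contact. The primary outcome is not affected.

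**What to change.** 1. Add one identical adverse-event question, covering the time since the last assessment, for every patient and partner in both arms at Mid, Post, 3 and 6 months. Enter it in Sections 4.2 and 4.3 and in Table 3.
2. Record the source of each event: shared assessment, therapy session or other.
3. In Section 5.3, keep the full count of those affected. Beside it, show partner counts by arm from the shared assessments, identify session-only events separately, and note that CBT-E partners have no session source. The full count should stay because a table limited to the shared source would drop real UNITE partner events.
4. Section 6 describes treatment delivery in the past tense, so some visits may be over. For those, classify events by source where records allow, and label the table descriptive with unequal ascertainment.

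The handling of individual cases stays as it is. The cost is about a minute per assessment and one extra column in the safety table. A new question cannot recover events missed at completed visits.
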